2.2 Treatments

The dose titration scheme for each study visit and telephone visit is shown in Figure 1 (amendment 1) and Figure 2 (amendment 2) and described below.

All subjects enrolled into the treatment period will receive open-label active treatment with nevanimibe HCl orally, starting at a dose of 1000 mg BID (amendment 1) or 500 mg BID (amendment 2). The first dose of nevanimibe HCl will be given at the study site at Visit T1 (Day 1; Enrollment). All subjects will receive nevanimibe HCl 1000 mg BID (amendment 1) or 500 mg BID (amendment 2) for Treatment Period Weeks 1-4 (Day 1 to Day 28). At Visit T2 (Day 29), all subjects will have their nevanimibe HCl dose automatically up-titrated to 1500 mg BID (amendment 1) or 1000 mg BID (amendment 2).

Predose serum 17-OHP levels will be assessed at every visit. Following Visits T2 and T3 (amendment 1) or Visits T2, T3 and T4 (amendment 2), a post-visit telephone visit will be performed once the serum 17-OHP results from the most recent on-site study visit are available (~10 days after study visits), at which time assessments for dose adjustments will be made based on 17-OHP results. If the 17-OHP level is $\leq 2x$ ULN (primary endpoint met), subjects will have their nevanimibe HCl dose down-titrated to the dose at which they met the primary endpoint

The highest available dose of nevanimibe will increase at each study visit, up to a maximum dose of 2000 mg BID at Visit T3 (amendment 1) or Visit T4 (amendment 2). Non-responders (i.e., subjects who did not meet the primary endpoint) will continue to undergo dose escalations at each visit. Responders (i.e., subjects who met the primary endpoint) will be treated with the dose at which they most recently met the primary endpoint. If the 17-OHP level is $>2x$ ULN at a visit after a subject had previously met the primary endpoint, a dose escalation will be performed during the telephone visit, and the subject is now considered a non-responder. Hence, a dose escalation will automatically be performed at the next on-site visit along with the other non-responders. This scenario is a possibility for Visit T3 (amendments 1 and 2) and Visit T4 (amendment 2 only).

In addition to the pre-defined titration scheme, nevanimibe HCl may also be down-titrated by the Investigator, if needed based on safety and tolerability, with approval of the Medical Monitor.

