- ⁱ Subjects with a 17-OHP level from Visit S1 $< 4x$ ULN (Cohort 2) and a daily maintenance GC dose \geq the equivalent of approximately 12 mg hydrocortisone/m² body surface area (see Appendices 2 and 3) will be contacted approximately 2 weeks after Visit S1 to have their GC dose decreased by the equivalent of approximately 5 mg hydrocortisone or 1 mg prednisone or prednisolone. They will then return for Visit S2 at least 2 weeks later. If their 17-OHP level from Visit S2 is $\geq 4x$ ULN, they will enter the Baseline period; if not, the case should be discussed with the Medical Monitor.
- ^j All subjects will undergo an up-titration of study drug dose at Visit T2, and subjects whose predose serum 17-OHP levels obtained at the most recent scheduled treatment period visit did not meet the primary endpoint will also undergo an up-titration of study drug dose at Visits T3 and T4. Approximately 2 weeks after each of these visits, the Investigator will review the laboratory results from the visits and determine whether the subject should continue their existing dose of nevanimibe HCl or have their dose titrated.
- ^k At Visits T1, T2, T3, T4, and T5/EoT, a trough ("0-hour") PK level and a serum storage sample will be collected within 30 minutes prior to dosing, and plasma for PK assessments will also be collected 1, 2, 3, and 4 hours postdose.
- ^l AEs will be collected from the time the subject signs the informed consent form until the last study visit or 30 days after the last dose of study drug, whichever is later.
- 17-OHP: 17-hydroxyprogesterone; A4: androstenedione; ACTH: adrenocorticotrophic hormone; AE: adverse event; aPTT: activated partial thromboplastin time; ECG: electrocardiogram; EoS: End-of-Study; EoT: End-of-Treatment; ET: early termination; GC: glucocorticoid; INR: international normalized ratio; MC: mineralocorticoid; P: progesterone; PE: physical examination; PK: pharmacokinetic(s) (samples); PT: prothrombin time; T: testosterone; tel: telephone visit

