7.1 Descriptive Statistics

The default summary statistics for quantitative variables will be the number of non-missing observations (n), mean (arithmetic or geometric (if applicable for pharmacokinetic data)) and/or median, standard deviation (SD) and/or quartiles (Q1 and Q3), minimum (min) and maximum (max) for those patients with data available.

For qualitative variables, the number (n) and percentage (%) of patients with non-missing data per category will be the default summary presentation, and where appropriate and present, the number of missing values as a “Missing” category. Percentages will be calculated using a denominator of all patients in a specified population or treatment group. The denominator will be specified in a footnote to the tables for clarification if necessary.

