7.7 Evaluation of Safety Endpoints

All safety variables will be evaluated for the safety population (SP). The analyses of treatment-emergent adverse events (TEAEs) will be performed overall and for subjects enrolled under global

amendment 1 and global amendment 2 separately. The analysis on the SOC and PT level will be repeated for the All Screened population to cover all AEs, also those recorded prior to first treatment with the study drug.

Treatment-emergent adverse events (TEAEs) will be summarized overall and by causal relationship and severity. TEAEs will be coded using the latest MedDRA version at the time of database close. Incidences and percentages will be provided on the subject-level (n), overall as well as on the system organ class (SOC) level and on the preferred term (PT) level for all subjects and by nevanimibe dose category. Results will additionally be prepared by time range. The suitable time ranges will be selected during the DRM for Cohort 1. A subject with more than one AE overall or assigned to one SOC or assigned to one PT will be counted once for the worst category (causal relationship or severity) on the subject level. For the summarization by relationship to study drug, the relationship will be categorized as “related” and “not related,” where related AEs are those with at least a possible relationship to the study treatment. For the summarization by nevanimibe dose, subjects with more than one AE overall or assigned to one SOC or assigned to one PT will be counted once on the subject level at the lowest nevanimibe dose category on which they experience the AE (i.e., a subject with two AEs, one when treated with 1000 mg BID and one when treated with 1500 mg BID, will be counted once at the 1000 mg BID dose). Additionally, the number of AEs per patient-year of treatment will be calculated by nevanimibe dose as (sum of number of AEs of subjects at the respective nevanimibe dose) / (patient-years of treatment at the respective nevanimibe dose).

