The mean time to onset of AEs (including worsening of preexisting conditions) will additionally be presented using summary statistics for continuous variables, overall and by SOC and PT. Time to first treatment-related TEAE and/or onset of selected TEAEs/groups of TEAE, may further be displayed in a Kaplan-Meier curve(s), by dose and/or in total, and by cohort and in total, where the time reflects the number of days since first being treated with the corresponding dose and changes to the dose will be included as censored information. If a subject is treated at a certain dose, then the dose is changed and at a later point, the subject is treated with the same dose again, then the duration of treatment with said dose will be added to the initial treatment period. Serious adverse events (SAEs) as well as AEs leading to death or discontinuation will be listed. Additionally, SAEs will be summarized overall and by nevanimibe dose.

Laboratory assessments, physical examinations, ECG and vital signs will be evaluated as continuous or categorical variables according to standard summary statistics for each visit, overall. Changes from baseline will be calculated for continuous variables and shift tables depicting the change from baseline will be produced for categorical variables where applicable and meaningful.

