14.2.3.1	Serum Androstenedione Concentration, by Visit
14.2.3.2	Summary of Serum Androstenedione, by Visit
14.2.4	Serum Progesterone, by Visit
14.2.5	Total Testosterone, by Visit
14.2.6	11-keto Testosterone, by Visit

- 14.3 Safety Data
 - 14.3.1 Adverse Events
 - 14.3.1.1 Overview of Treatment-Emergent Adverse Events, by Dose Level and Overall
 - 14.3.1.2 Treatment-Emergent Adverse Events by Dose Level and Overall
 - 14.3.1.2.1 Treatment-Emergent Adverse Events by Dose Level and Overall, by Preferred Term, Alphabetically
 - 14.3.1.2.2 Treatment-Emergent Adverse Events by Dose Level and Overall, by Preferred Term, by Frequency
 - 14.3.1.3 Treatment-Emergent Adverse Events by Dose Level and Overall, by Time Range
 - 14.3.1.4 Treatment-Emergent Adverse Events by Dose Level and Overall, by System Organ Class and Preferred Term, and Maximum Severity
 - 14.3.1.5 Treatment-Emergent Adverse Events Related to Study Drug by Dose Level and Overall, by System Organ Class and Preferred Term
 - 14.3.1.6 Treatment-Emergent Adverse Events Related to Study Drug by Dose Level and Overall, by System Organ Class and Preferred Term, and Maximum Severity
 - 14.3.1.7 Average Time to Treatment-Emergent Adverse Event
 - 14.3.2 Serious Adverse Events and Adverse Events Leading to Death or Discontinuation
 - 14.3.2.1 Listing of Treatment-Emergent Serious Adverse Events
 - 14.3.2.2 Listing of Treatment-Emergent Adverse Events Leading to Discontinuation from Study
 - 14.3.2.3 Listing of Treatment-Emergent Adverse Events Leading to Death
 - 14.3.3 Other Safety Parameters
 - 14.3.3.1 Blood Chemistry
 - 14.3.3.2 Plasma ACTH and Serum Cortisol
 - 14.3.3.3 Hematology
 - 14.3.3.4 Coagulation Parameters
 - 14.3.3.5 Urinalysis
 - 14.3.3.6 Salivary Cortisol and Progesterone
 - 14.3.3.7 Blood Chemistry, Shift Tables
 - 14.3.3.7.1 Blood Chemistry, Shift Tables, Part 1
 - 14.3.3.7.2 Blood Chemistry, Shift Tables, Part 2

Listings

- 16.1 Subject Data Listings
 - 16.1.1 Study Subjects
 - 16.1.1.1 Disposition of Subjects
 - 16.1.1.1.1 Screening Failures
 - 16.1.1.1.2 Study Progress Overview

16.1.1.1.3	Site Numbers and Principle Investigators
16.1.1.1.4	Visit Dates and Discontinuation
16.1.1.2	Eligibility and Protocol Deviations
16.1.1.2.1	Subjects with Violation of Inclusion / Exclusion Criteria
16.1.1.2.2	Protocol Deviations and Other Reason for Exclusion from Analysis Sets, Assignment to Analysis Sets
16.1.1.3	Demographic Data and Other Baseline Characteristics

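### SAP 7.7's lowest-dose counting rule can only lower the TEAE incidence shown at higher doses, and does so where AEs recur in the same row across doses

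*SAP*

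**What the plan says.** SAP 7.7 sets two counting rules for TEAEs in the same paragraph.

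- For summaries by relationship or severity, a subject with several AEs overall, in one SOC or in one PT is "counted once for the worst category (causal relationship or severity) on the subject level".
- For summaries by dose, such a subject is "counted once on the subject level at the lowest nevanimibe dose category on which they experience the AE". The worked example has one AE at 1000 mg BID and one at 1500 mg BID, and counts the subject only at 1000 mg BID.

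SAP 7.1 fixes the percentage base: "Percentages will be calculated using a denominator of all patients in a specified population or treatment group". It does not take out subjects already counted at a lower dose.

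Subjects pass through several doses. SAP 2.3 (Table 2, footnote j) states "All subjects will undergo an up-titration of study drug dose at Visit T2", and non-responders continue upward. Doses can also come down, either because the 17-OHP target was met or because, in SAP 2.2, "nevanimibe HCl may also be down-titrated by the Investigator, if needed based on safety and tolerability".

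The SAP also plans AEs per patient-year by dose (7.7), optional Kaplan-Meier curves by dose (7.7, with Figure 14.3.1.7 listed in Appendix 1), and listings of SAEs and of AEs leading to death or discontinuation. Protocol 9.6.2 asks for TEAEs by dose and contains no lowest-dose rule.

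**The concern.** SAP 2.5 asks whether the higher doses still have an adequate safety profile, and the by-dose TEAE tables are where a reader will look for the answer. A rule that assigns each subject to the lowest affected dose takes subjects out of the higher-dose columns and never adds any. If AEs recur, a constant risk is displayed as one that falls with dose. Protocol 3.2 says earlier experience suggests tolerability improves with longer dosing, so such a pattern could be read as confirmation.

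The rule also says lowest, not first. A subject who has an AE at a higher dose, is titrated down and then has another AE in the same row disappears from the higher-dose column, even though the AE appeared there first.

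**Working it through.** **The SAP's own example.** AEs at 1000 and 1500 mg BID. The SAP rule gives 1 subject at 1000 and 0 at 1500. Counting within each dose gives 1 and 1. The stated result is reproduced, and the 1500 mg BID event is absent from its column.

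**Inputs.** From the SAP: the counting rule (7.7), the denominator (7.1), the four dose levels (2.1) and a sample of 20-24 (2.9). Assumed, because the documents give no AE rates: a probability p_k of an AE in the row at dose step k, all four doses taken in ascending order, and a share c of subjects in whom AEs can be recorded anew at later doses, independently of earlier ones. The remaining subjects have at most one record in the row. Since everyone takes every dose here, a denominator of all subjects and one of exposed subjects coincide.

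**Formulas.** Let F_k be the product of (1 − p_j) over all lower doses j.

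- Displayed at dose k = p_k × F_k
- Actual at dose k = p_k × [c + (1 − c) × F_k]
- Share missing = 1 − displayed/actual

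**Flat 30%.** F = 1, 0.7, 0.49, 0.343.

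| | 500 | 1000 | 1500 | 2000 mg BID | Missing at 2000 |
|---|---|---|---|---|---|
| Displayed, any c | 30% | 21% | 14.7% | 10.3% | – |
| Actual, c = 0 | 30% | 21% | 14.7% | 10.3% | 0 |
| Actual, c = 0.5 | 30% | 25.5% | 22.4% | 20.1% | 49% |
| Actual, c = 1 | 30% | 30% | 30% | 30% | 66% |

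For example, at 2000 mg BID with c = 0.5, actual = 0.30 × (0.5 + 0.5 × 0.343) = 20.1%. Actual incidence is itself falling in that row, so only part of the displayed fall comes from the rule. It is wholly due to the rule only at c = 1.

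**Other assumed rates, c = 1.**

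- Flat 10%: shown as 10/9/8.1/7.3%.
- Rising 20/30/40/50%: shown as 20/24/22.4/16.8%, so a rise becomes a fall after the second step.
- Rare, 2/3/4/5%: shown as 2/2.9/3.8/4.6%, almost unchanged.
- Amendment 1 path (1000/1500/2000 mg BID), flat 30%: shown as 30/21/14.7%.

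**In subjects.** With N = 24 and p = 0.30, the columns show 7.2, 5.0, 3.5 and 2.5, against 7.2 at each dose if c = 1. This is an upper-end illustration: responders stay at a lower dose, so fewer than 24 would be expected to reach 2000 mg BID.

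**Where the two rules meet.** Appendix 1 lists Table 14.3.1.4, "Treatment-Emergent Adverse Events by Dose Level and Overall, by System Organ Class and Preferred Term, and Maximum Severity", and Table 14.3.1.6 does the same for related events. Take a mild AE at 1000 mg BID and a severe AE of the same PT at 1500 mg BID:

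- worst first, keeping its dose: severe at 1500;
- lowest dose first: mild at 1000;
- each rule applied separately: severe at 1000, which did not occur.

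The visible SAP text does not choose between these three cells.

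**The case against.** The strongest reply is that the by-dose table is not the only display. A reader might infer that the plan as a whole cannot separate this artefact from a genuine improvement with time. The documents do not support that. AEs per patient-year by dose count every event, so under a flat risk with independent recurrence the rate would stay flat, while a real improvement would lower it. The Kaplan-Meier time runs from first treatment at each dose, with dose changes censored, so an event at 2000 mg BID need not be absorbed by one at a lower dose. This stands for the any-TEAE row. It does not close the gap elsewhere: none of these displays is stated to give subject incidence by dose at SOC, PT or severity level, and the text of 7.7 makes the curves optional.

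A reader might also infer that the severity tables are undefined. That goes too far. The SAP refers to mock tables that are not among the documents and may settle the order of the two rules.

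Finally, placing an AE at the lowest dose at which it appears is an openly stated descriptive choice, in a study with no safety targets and no inferential safety analysis. That is fair, and it limits how serious the point is. It does not make the resulting percentages incidences at the higher doses.

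**Conclusion.** The point holds as a should-fix matter. Relative to counting within each dose, the SAP 7.7 rule can only reduce higher-dose subject incidence, and the SAP's own example shows it doing so. The exposure is confined to rows in which the same subject has separate AE records at more than one dose: chiefly any-TEAE, SOC rows and common recurring PTs. A single continuing AE is not affected, rare terms barely move, and the loss is zero without repeats.

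The size is illustrative only. At an assumed flat 30%, between none and about two thirds (66%) of the subjects with an AE at 2000 mg BID would be missing from that column, depending on recurrence. That range rests on assumed rates, all four doses being taken, and independence between doses; the documents do not allow an estimate for this trial. The Overall column and the 40% success rule are untouched.

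The unstated order of the worst-category and lowest-dose rules is a secondary point, held with less confidence because of the unseen mock tables.

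**What to change.** Reword SAP 7.7 for all by-dose TEAE and SAE summaries:

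- Count a subject once per row (any AE, SOC, PT) within each dose category at which an AE began or worsened.
- Take maximum severity and relationship within that dose category.
- Use the number of subjects exposed to that dose as the denominator.
- Keep once-per-subject counting for the Overall column only.

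Say explicitly that this covers the SAE statement in 7.7 ("Additionally, SAEs will be summarized overall and by nevanimibe dose") and Table 14.3.1.3 ("Treatment-Emergent Adverse Events by Dose Level and Overall, by Time Range"), since neither is stated to be inside or outside the present rule. Bring the mock tables into line.

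The cost is SAP wording, table programming and footnotes, with no new data and no change in conduct. The footnotes should say that dose columns do not add to Overall and that dose remains confounded with time on study. They should also say that worsening within one AE record stays at its onset dose unless recorded as a new AE, because Protocol 6.10.2 asks for the maximum severity of each AE. Patient-year rates by SOC or PT are optional: 24 subjects × 16/52 is about 7.4 patient-years in total, so they would be sparse by dose.

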2.1 Study Design

This is a multicenter, intra-subject dose-titration open-label study of nevanimibe hydrochloride (HCl) for the treatment of classic congenital adrenal hyperplasia (CAH). Following a Screening Period, eligible subjects will enter a Baseline and a Treatment Period. During the Treatment Period, subjects will receive nevanimibe HCl twice daily (BID) for 12 or 16 weeks, according to the protocol version (amendment 1 or amendment 2, respectively). Subjects will begin dosing with nevanimibe HCl 1000 mg or 500 mg BID (amendment 1 or amendment 2, respectively). Titration of nevanimibe HCl will depend upon the 17-OHP response, which will be assessed every 4 weeks during the Treatment Period. The dosing regimens are intended to achieve and maintain $17\text{-OHP} \leq 2x$ the upper limit of normal (ULN) (the primary endpoint) on the lowest possible dose of nevanimibe HCl while actively up-titrating if $17\text{-OHP} > 2x$ ULN. Thus, subjects who are found to have met the primary endpoint (i.e., on the previous lower dose of nevanimibe HCl) based on their most recent serum 17-OHP value will have their nevanimibe HCl dose down-titrated to the dose on which they met the endpoint. Four doses of nevanimibe HCl (500 mg BID, 1000 mg BID, 1500 mg BID, and 2000 mg BID) are available for use in the study. The visit and dosing schedules are schematically depicted for amendments 1 and 2 below (Figure 1 and Figure 2).

prednisolone per day. They will then return for Visit S2 to have their 17-OHP level rechecked approximately 2 to 4 weeks after their glucocorticoid dose was changed. If their serum 17-OHP level from Visit S2 is $\geq 4x$ ULN, they will proceed to the Baseline Visit (Visit B1). If not, the case should be discussed with the Medical Monitor.

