2.5 Study Hypothesis

The hypotheses to be investigated by this study include whether sustained, continuous dosing of nevanimibe HCl will result in greater efficacy than observed in the previous Phase 2 CAH study (ATR-101-201) and whether higher doses are needed. Additionally, it will be evaluated whether the higher doses used in this study still have a sufficient safety profile. The primary efficacy endpoint will be evaluated by means of the percentage of subjects achieving predose serum 17-OHP targets as follows:

- Men and postmenopausal women: 17-OHP $\leq 2 \times$ ULN
- Premenopausal women in follicular phase: 17-OHP $\leq 2 \times$ follicular phase ULN
- Premenopausal women in luteal phase: 17-OHP $\leq (2 \times \text{follicular phase ULN} + (\text{luteal phase ULN} - \text{follicular phase ULN}))$

The responder rate (percentage of subjects achieving the predose serum 17-OHP targets) for Cohort i ($i=1, 2$) will be calculated as follows:

$$\text{Responder rate}_{Ci} = \frac{\text{Number of responders in } Ci}{N_{Ci}} \times 100\%$$

with Ci being the corresponding cohort. The responder rate will also be calculated overall.

The study will be considered positive if 40% or more of enrolled subjects in either cohort were classified as responders at any of the four visits T2 (Day 29), T3 (Day 57), T4 (Day 85) or T5 (Day 113; Amendment 2).

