6.3 Secondary Efficacy Endpoints

The following are secondary efficacy endpoints:

-Androstenedione, progesterone, total testosterone, and 11-ketotestosterone levels as measured at Baseline, Visit T2 (Day 29), Visit T3 (Day 57), Visit T4 (Day 85), Visit T5 (Day 113; Amendment 2) and Follow-up Visit (Day 113 (Amendment 1) or Day 141 (Amendment 2)); and change from Baseline to Visit T2 (Day 29), Visit T3 (Day 57), Visit T4 (Day 85), Visit T5 (Day 113; Amendment 2) and Follow-up Visit (Day 113 (Amendment 1) or Day 141 (Amendment 2)).

-Serum 17-OHP levels as measured at Visit T1 (Day 1), Visit T2 (Day 29), Visit T3 (Day 57), Visit T4 (Day 85), and Visit T5 (Day 113; Amendment 2) at h0, h1, h2, h3 and h4 (predose and 1-4 hours after administration of the morning replacement glucocorticoid, mineralocorticoid (if applicable), and/or study drug (if applicable) doses); and change from baseline (Visit T1 (Day 1)) to Visit T2 (Day 29), Visit T3 (Day 57), Visit T4 (Day 85), Visit T5 (Day 113; Amendment 2).

-Salivary 17-OHP levels as measured at Visit T1 (Day 1), Visit T2 (Day 29), Visit T3 (Day 57), Visit T4 (Day 85), and Visit T5 (Day 113; Amendment 2) (at time points h0, h2 and h4 (just before, 2 hours after, and 4 hours after (respectively) administration of the morning replacement glucocorticoid (if applicable), mineralocorticoid (if applicable) and/or study drug (if applicable) doses)) and change from Baseline (Visit T1 (Day 1)) to Visit T2 (Day 29), Visit T3 (Day 57), Visit T4 (Day 85), and Visit T5 (Day 113; Amendment 2).

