7.3 Calculation of Study Days and Durations

Study days and, if applicable and meaningful, durations will be determined by comparing the respective date to the date of first dose of study drug.

- If the respective date is on or after date of first dose of study drug:
$$\text{Study day/Duration} = (\text{Date (e.g., date of visit)} - \text{Date of first dose of study drug}) + 1$$
- If the respective date precedes the date of first dose of study drug:

Study day/Duration = Date (e.g., date of medical history event) - Date of first dose of study drug

Time to onset and duration of adverse events will be calculated as follows:

- Time to onset = start date of AE - date of first dose of study drug [+1 for AE starting on or after date of first dose of study drug]
- Duration of adverse event = (stop date - start date) + 1

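### Table 14.3.1.7 averages time to onset only over adverse events that occurred and from first dose, so it tracks follow-up length and cannot show onset after a dose increase; the curve that could is left optional

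*SAP*

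**What the plan says.** SAP 7.7 plans this summary overall and by system organ class and preferred term: "The mean time to onset of AEs (including worsening of preexisting conditions) will additionally be presented using summary statistics for continuous variables". SAP 7.3 sets the clock: "Time to onset = start date of AE - date of first dose of study drug", plus one day for events on or after that date. SAP Appendix 1 lists the output as Table 14.3.1.7, "Average Time to Treatment-Emergent Adverse Event". The titles of Tables 14.3.1.1 to 14.3.1.6 all refer to dose level; this one does not.

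No censoring rule and no restart of the clock is given for the mean. The default for continuous summaries in SAP 7.1 is to report statistics such as "minimum (min) and maximum (max) for those patients with data available", so subjects without the event do not enter.

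The design has two features that matter here. Length of treatment varies: "nevanimibe HCl twice daily (BID) for 12 or 16 weeks, according to the protocol version". The last visit differs accordingly: "Follow-up Visit (Day 113 (Amendment 1) or Day 141 (Amendment 2". Dose also rises over time. SAP 2.2 says "At Visit T2 (Day 29), all subjects will have their nevanimibe HCl dose automatically up-titrated", with further increases for non-responders at later visits.

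The same paragraph of SAP 7.7 says that Kaplan-Meier curves *may* be shown for the first treatment-related event or for selected events, counting from first treatment at the dose concerned and censoring at dose changes. Appendix 1, which introduces its lists as required outputs, includes Figure 14.3.1.7: time to first treatment-emergent event, by dose, with no restriction to related events.

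**The concern.** SAP 2.5 raises a safety question alongside efficacy: "it will be evaluated whether the higher doses used in this study still have a sufficient safety profile". For timing, the useful information is whether events start soon after a dose increase, and when first events occur among everyone at risk. Table 14.3.1.7 gives neither.

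A mean over events that occurred is bounded by the observation window and, for uncommon events, sits near its midpoint whatever the risk. A clock started at first dose records an event that begins 3 days after the Day 85 increase as onset on Day 88. A reader of the study report could take a figure of six or seven weeks as evidence of late onset when it reflects the visit calendar.

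**Working it through.** The documents state no expected onset time, so there is no plan figure to reproduce. The event rates and lags below are assumptions chosen to show how the table behaves.

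**Inputs from the documents.** Last visit on Day 113 (Amendment 1) or Day 141 (Amendment 2), SAP 6.3. Adverse events are collected to the last visit or 30 days after last dose, whichever is later, which adds about two days and changes little. Scheduled dose starts are Days 1, 29 and 57 (Amendment 1) and Days 1, 29, 57 and 85 (Amendment 2), SAP 2.2.

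**1. Dependence on follow-up.** With a constant hazard λ, the mean first-onset time among subjects whose event occurs by day T is

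E[X | X ≤ T] = 1/λ − T·exp(−λT) / (1 − exp(−λT)).

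At λ = 0.0016 per day:
- T = 113: 625 − 113 × 0.8346/0.1654 = 54.8 days.
- T = 141: 625 − 141 × 0.7980/0.2020 = 67.9 days.

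The hazard is identical, yet the mean moves by 13 days because follow-up differs by 28.

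Other assumed rates, per patient-year:

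| Rate | Day 113 | Day 141 | Unconditional mean |
|---|---|---|---|
| 0.25 | 55.8 | 69.4 | 1461 |
| 1 | 53.6 | 66.0 | 365 |
| 3 | 47.9 | 57.2 | 122 |
| 6 | 39.9 | 45.4 | 61 |

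A 400,000-draw simulation at 1 per patient-year gave 53.5 and 65.9. If every event rather than the first is averaged, a constant rate gives exactly T/2: 56.5 and 70.5 days.

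**2. Weak dependence on risk.** With T = 141, cumulative incidences of 20%, 50% and 80% give means of 67.9, 62.4 and 52.4 days. A fourfold change in risk moves the mean by 15.5 days. With T = 113 the means are 54.4, 50.0 and 42.0.

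**3. Dose steps.** Place one event 3 days after each scheduled dose start and apply the SAP 7.3 count:
- Amendment 1: Days 4, 32, 60; mean 96/3 = 32 days, SD 28.0.
- Amendment 2: Days 4, 32, 60, 88; mean 184/4 = 46 days, SD 36.1.

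On a clock restarted at each step, every one of these is day 4. Lags of 1 and 7 days give means of 30 and 36 (Amendment 1) and 44 and 50 (Amendment 2).

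With a random lag (exponential, mean 4 days, steps equally likely), the mean is the average step day plus 4: 43 + 4 = 47 days for four steps and 29 + 4 = 33 for three. In that model 83% of events begin within 7 days of a step.

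**4. The two descriptions of the curve.** SAP 7.7: optional; treatment-related or selected events. Appendix 1, Figure 14.3.1.7: in the required list; first treatment-emergent event of any kind, by dose. These differ in both status and scope.

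**The case against.** The strongest reply is that this table is an extra in a plan that looks at dose and timing elsewhere. SAP 7.7 has treatment-emergent events by dose category, by time range and per patient-year at each dose, and serious events by dose. It runs the analyses overall and separately by amendment, so the two follow-up lengths are not only pooled. Figure 14.3.1.7 keeps event-free subjects in the risk set and starts the clock at the dose concerned. Medians, quartiles and ranges may accompany the mean, and SAP 7 calls all summaries exploratory.

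Most of this stands, and it rules out three stronger readings:

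- A reader might infer that the safety plan conceals onset after escalation. It does not; the limitation belongs to this table, and the dates remain in the data.
- A reader might infer that the table cannot separate a step-triggered event from a steady background event. The illustrations do not support that as a general statement: 47 days against 52 to 68 under Amendment 2, and 33 against 42 to 54 under Amendment 1. The figures do meet at a high steady rate (45.4 days at 6 per patient-year, against 46 for a 3-day lag).
- A reader might infer that the step illustration predicts the trial's result. Responders are not stepped up at later visits and lapsed responders are stepped up at telephone visits, so equal weight on the scheduled days is a simplification.

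The other outputs still leave a gap. By-dose tables show at which dose an event occurred, not how soon after a step, and subject-level counts go to the lowest dose with the event. Time ranges are left to the Cohort 1 data review meeting. By-amendment analysis removes the mixing of windows but neither the conditioning on an event nor the first-dose clock. The figure would do most of the work, but SAP 7.7 does not commit to it, and Appendix 1 says that numbering and titles are not obligatory.

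**Conclusion.** The point holds for Table 14.3.1.7. Its clock and the restriction to events that occurred follow from SAP 7.3, 7.7 and 7.1; the restriction is implied rather than stated in those words. The mean depends heavily on follow-up (about 55 against 68 days at one assumed hazard) and cannot show whether events follow a dose increase. The remedy largely exists already, but with inconsistent status and scope between SAP 7.7 and Appendix 1.

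Severity is minor. This is a descriptive safety display and has no bearing on the primary endpoint, the analysis populations or the 40% rule. The sizes rest on assumed constant hazards and assumed lags; the direction does not.

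**What to change.** 1. In SAP 7.7, commit to the Kaplan-Meier or cumulative-incidence display by changing *may* to *will*. Align its scope with Figure 14.3.1.7 (first treatment-emergent event of any kind, by dose), and state that event-free subjects stay in the risk set.
2. In Table 14.3.1.7, replace the mean from first dose with the number of treatment-emergent events and the patient-days at risk by days since the most recent dose increase, counting Day 1 as the first. Suitable bands are days 1–7, 8–14, 15–28 and over 28. Present this overall, or for frequent system organ classes only. Show time after a down-titration, during a drug holiday and in off-drug follow-up separately.
3. If cumulative incidence from first dose is reported, give it pooled to Day 84, and to Day 112 for Amendment 2 subjects only, because Amendment 1 treatment ends at 12 weeks.
4. If any mean is kept, footnote that it is conditional on an event and depends on length of follow-up.

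The cost is a few lines of SAP text, one derived variable (dose-change dates are already needed for the by-dose tables) and one reprogrammed table. With about 20–24 subjects some cells will be sparse, which is why a full breakdown by preferred term is not proposed.
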